I will receive focused training in predictive modeling, with an emphasis on recursive partitioning machine learning methods: classification and regression trees (CART) and random forests (RF). Our original analytic plan proposed that regression trees would be grown to examine the predictive structure of explanatory variables (including PBCM treatment condition) with respect to the following continuous outcomes: (1) % cocaine-negative urines during CM, (2) % CM sessions attended, (3) % days of any self-reported substance use during CM, and (4) % days of self-reported stimulant use during the 6 months following CM. CART involves partitioning observations into more homogenous subgroups with respect to the outcome of interest by identifying cut points along predictor variables. For each CART, cost-complexity pruning would be conducted using five-fold cross validation to limit overfitting. A Random Forest (RF) approach would subsequently be implemented with each set of predictors and outcomes to objectively evaluate the relative importance of each predictor and optimize overall model performance. RF involves growing an ensemble of decision trees based on bootstrapped samples of observations and predictors to increase tree diversity. This method includes internal cross-validation using out-of-bag error rates (based on observations not included in the bootstrap sample) to limit overfitting during model training and performs well without excessive tuning of model parameters. Taken together these data mining approaches would provide deep insight into interrelationships between predictors and outcomes of interest and could also be further examined through a resource-constrained Tabu search procedure to develop multiple regression models forecasting treatment response (% cocaine-negative urines) in each PBCM variant, while penalizing individual predictors based

on measurement cost.¹⁰³ Resource-constrained Tabu search has not previously been used to analyze the predictive utility of neuromarkers in view of the increased cost of measuring these signals but is ideally suited to this issue in measurement-based care. In our revised approach, we employed longitudinal logistic regression as described above and specifically examined outcomes on a per session basis, with provision of a cocaine-negative specimen at the session being considered a successful outcome and cocaine-positive or missing specimens considered unsuccessful. This revised approach enables more efficient use of the available data by capturing the full trajectory of participant responses over time through repeated measures modeling, rather than relying on a single aggregated outcome.

Missing Data Strategies: Recursive partitioning approaches (CART, RF) flexibly handle missing data for candidate predictors through several heuristic and/or interpolation based approaches. Missing data handling for TABU search is not yet well-characterized but works well, provided that missing data is randomly distributed and relatively rare. Expecting a 15% rate of attrition, usable substance use outcome data is anticipated for a minimal sample size of $n = 119$ CM recipients. Additional outcome variables will be derived from chart review (e.g., treatment engagement, urinalysis results), providing additional options for quantifying outcomes, not contingent on participation in study check-in appointments. Importantly, all methods specified above can be used with binary outcomes (i.e., CM-completer versus CM-non-completer). Consequently, while efforts will be made to collect detailed outcome data on each participant (and this appears feasible on the basis of my ongoing pilot project), primary predictive modeling aims can be accomplished under circumstances of high attrition and data loss. Our revised analytic approach has also been configured to be resilient to missingness through handling missing specimens as unsuccessful outcomes using an intent-to-treat approach. Where necessary (e.g., for treatment trajectories impacted by the pandemic), a Bayesian logistic regression model can also be used to impute missing values based on observed patterns to estimate likely values for unobserved responses.

Specific Aim 2. Evaluate longitudinal change in cognitive-behavioral and EEG-based indices of FMDM during CM. Engagement in PBCM will be associated with differential enhancement of control-related theta synchronization between ACC and IPFC during high conflict events in the Parametric Conflict Flankers task, relative to PBCM nonadherence and will also foster greater improvement in working memory and episodic future thinking effects on delay discounting (Hypothesis 2a). Individual differences in treatment response trajectory during CM will also be explored as a factor in neuroadaptive change during treatment (Exploratory Sub-Aim).

Increased functional connectivity within control-related brain networks in conjunction with CM would reflect important mechanisms of neural recovery facilitated by this intervention. I will receive training in functional connectivity analysis of EEG data, which may include a series of learning experiences guided by my co-mentor, [name], and consultants, Drs. [name], [name], and [name]. Most importantly, I will receive training in synchronization likelihood, a nonlinear approach to estimating functional connectivity which measures statistical dependencies in dynamic time series and can thus characterize both linear and nonlinear interdependencies in EEG data. This technique may be applied to evaluate synchronization strength between pairs of electrodes and within frequency bands, based on a priori hypotheses, although more traditional functional connectivity measures may also be utilized. Specifically, theta frequency synchronization between ACC and IPFC electrode sites will be computed to quantify transient network dynamics related to control modulation. Treatment-related change in

executive working memory and delay discounting behavior will also be evaluated as cognitive-behavioral indicators of FMDM-related function.

Repeated measures analysis of covariance (ANCOVA) will be conducted to evaluate treatment-related change in the following indices of FMDM between PBCM adherent and non-adherent: (1) control-related theta synchrony between ACC and IPFC, (2) Brown-Peterson working memory score, and (3) change in the episodic future thinking effect in delay discounting slopes ($\Delta \ln(k)$). A general linear model design will be utilized including assessment latency (baseline versus follow-up) as a within-subjects factor. In order to account for differences in substance use, adherence, and PBCM treatment condition, these factors (% days of use, % sessions attended, PBCM condition) may also be considered as covariates or between-subjects factors using a median split approach. Tukey's HSD (or equivalent) will be used for post hoc evaluation of marginal means to clarify main and interaction effects. Adjusted marginal means may be used to investigate covariates as moderators of the treatment-by-time interaction. Given the previously identified relationship between ACC-IPFC theta phase synchrony and amplitude of the ERN and conflict N2,66,67 treatment-related change in these ERPs may also be evaluated using the same approach. Correlations between ERN/N2 amplitudes and ACC-IPFC theta synchrony, as well between EEG and cognitive-behavioral measures, may also be computed for each timepoint to identify significant linear relationships between dependent measures. To account for the constraints of a reduced sample size, we may employ alternative statistical approaches as needed—particularly to address non-normality and other assumption violations that could compromise model validity.

Additional exploratory analyses may also be conducted to investigate trajectories of recovery during PBCM in relation to neuroadaptive change. I will receive specialized training in multilevel modeling approaches to longitudinal data analysis, including use of growth mixture models to resolve latent subgroups exhibiting distinct patterns of longitudinal change. For participants assigned to both PBCM conditions, longest duration of cocaine abstinence may be computed on a weekly basis from within-treatment urinalysis results and attendance (unexcused, missed appointments will also be considered to end a period of abstinence). Growth mixture modeling may subsequently be employed to evaluate intra-individual change in the longest duration of abstinence achieved during PBCM treatment and determine if distinct change profiles meaningfully represent inter-individual variance. If identified, subgroups exhibiting distinct trajectories in PBCM may also exhibit different patterns of neural recovery within functional connectivity networks underlying cognitive control and reward representation. Exploratory, network-based analyses may therefore also be conducted (if applicable) and may generate new insights into neuroadaptive processes that reflect and may also support sustained abstinence in CM. Cocaine users have previously been demonstrated to exhibit reduced interhemispheric functional connectivity within the dorsal frontoparietal control network, which is thought to support goal-directed top-down control of attention and behavior, as well as representation and anticipation of future rewards. My training in functional connectivity analysis of EEG data will support exploratory analysis of network-level disturbances in CUD, as well as potential treatment-related change in interhemispheric functional connectivity within the dorsal frontoparietal control network in relation to CM. Using methods previously described by my consultants, Drs. [name], [name], and [name], I may also employ synchronization likelihood to identify localized functional connectivity networks that significantly differ between CUD subgroups exhibiting different patterns of cocaine abstinence during CM. Briefly, pairwise synchronization likelihood will be computed between all pairs of EEG channels for reward- and control-

related epochs derived from Incentive Delay and Flankers tasks, respectively. Non-parametric, network-based statistics will subsequently be employed to identify pairings which differ significantly between CUD subgroups at baseline and follow-up, including potential differences in interhemispheric functional connectivity within the dorsal frontoparietal control network. Training offered by my consultants would also afford the opportunity to combine synchronization likelihood with graph theoretic approaches to functional connectivity analysis. Consequently, additional exploratory analyses can target differences in network-level properties within local (e.g., strength, local efficiency, betweenness centrality) and global (e.g., path length, small worldness, global efficiency) functional connectivity structures. However, it is noted that additional exploratory analyses can only be undertaken if the final sample size is sufficient to support them.

Missing Data Strategies: Individuals lost to follow-up will be excluded from these analyses due to necessary inclusion of longitudinal measures from the follow-up timepoint. It is anticipated that covariates of interest will be available for all individuals who complete the follow-up assessment session. Specifically, treatment engagement will be determined on the basis of chart review and self-reported substance use will be evaluated on a weekly basis. For participants who miss one or more check-in assessment during the treatment period, the timeline follow-back procedure will be extended to evaluate the full period between the present and previous study contact. In my previous longitudinal study of substance users, I was able to collect all necessary follow-up data on 80.8% of my originally enrolled sample. However, it is also possible that unexpected circumstances may require imputation of missing data values. In such cases imputation of missing values will leverage available within- and between-subjects data.

Additional exploratory analyses and quality assessment analyses will also be conducted over the course of the study. Consequently, the analysis plan outlined above will not cover all analyses that may be potentially undertaken with the current dataset. Similarly, additional approaches to data preprocessing (filtering, data reduction, artifact rejection, etc.) that are not described above may also be applied in order to optimize signal quality for the purposes of proposed and exploratory analyses. It is noted that, because of the nature of the current study (human subjects research, psychophysiological research), data points may not be reliably collected as prescribed for all participants and timepoints. For example, missing data may occur if a participant chooses to discontinue study procedures during an assessment visit due to fatigue or external obligations. Data loss may also occur due to equipment failure or other conditions results in poor quality data during psychophysiological recordings and cognitive-behavioral testing procedures.

View: 5 Sub-Studies

1.0 * Is there a sub-study or are there sub-studies associated with this study?

There is a sub-study (or there are sub-studies) associated with this study and VAPHS is participating.

View: 5.1 Sub-Studies

1.0 * Please describe the sub-study or sub-studies:

SUB-STUDY 1: FEASIBILITY OF CM TREATMENT VIA TELEHEALTH TREATMENT SESSIONS

Due to the current COVID-19 pandemic, it is possible that noncritical in-person outpatient visits will be discontinued if there is a surge in new cases in our local area. Given the nature of the current RTC, we are at risk of substantial data loss if CM treatment sessions offered through the current protocol must be terminated (as was the case in 3/2020). We would therefore like to conduct a sub-study to test the feasibility of conducting CM sessions via telehealth treatment sessions. Specifically, we will experiment with methods for delivering CM via VA Video Connect sessions. One or more Veterans will be provided with oral fluid point-of-care tests and will be trained on how to perform this type of objective testing during VVC sessions such that results can be remotely reviewed and prize draws rewarded accordingly. Participants in this case study will receive the standard voucher version of PBCM offered at VAPHS and prize vouchers will be delivered to or retrieved by Veteran following the remote session. Participants will additionally be asked to provide feedback on home-based point-of-care testing, methods for remotely conducted CM prize draws, prize transmissal, and other related aspects of remotely-delivered CM treatment. As described in the Substudy consent form, a combination of remote and in-person treatment sessions may be offered, depending upon the unique needs of each participant and/or barriers to remote implementation that may present over time.

Between 1-15 Veterans will be invited to take part in telehealth-based CM treatment sessions. We will specifically make an effort to invite individuals to participate for whom in-person CM sessions are not preferred because (1) the Veteran is at high risk for complications from COVID-19, (2) the Veteran is under quarantine due to COVID-positive status or housing-related restrictions, or (3) the Veteran has ongoing transportation problems that make attending in-person treatment sessions more difficult. All participants will be either be self-referred or clinician-referred to receive CM services and will meet general requirements for this type of treatment (e.g., ongoing problematic stimulant use). Participants must also be willing and able to participate in telehealth services, appropriate for telehealth care, and able to interact and communicate through audio and visual elements of the VVC platform. No other eligibility criteria will apply. Participants in the substudy may be former (e.g., completed or withdrawn) participants from the primary protocol or participants determined ineligible to participate in the primary protocol. Participants will not receive any compensation for participating other than prizes received in the course of treatment. Aside from the use of VA-approved telehealth technology to remotely conduct CM treatment sessions, the CM protocol to be used in this substudy will be identical to that prescribed by VHA's National CM Implementation effort. Importantly, similar adaptation of evidence-based treatment protocols to telehealth are (and have been) routinely conducted in the course of standard clinical care during the pandemic. There are also no significant risks associated with the proposed telehealth-based protocol - rather, it is expected that this CM option may be lower risk for some Veterans. Potential participants will be informed of this opportunity during either interactions with the research team regarding interest in the primary protocol (e.g., upon screening out) or during initial clinical interactions upon referral to CM if barriers to in-person attendance are identified. Participants will provide informed consent to participate in this substudy. Data collected will generally be limited to information typically acquired in the course of standard clinical administration of CM (i.e., self-reported use, substance use test results, attendance, etc.). However, we will additionally take note of any feedback from patients regarding the telehealth experience, as well as any technical or logistical problems that occur in the course of remote administration. The goal of this substudy will be to develop and refine methods for remote administration of PBCM should this become necessary in the future. The standard CM note template will be used to document such sessions in CPRS. All data collected for this substudy can be extracted from documentation of treatment sessions entered in the chart.

Risks and Benefits: With respect to Substudy 1, participants will have the opportunity to receive a telemedicine version of CM that is not otherwise available at our site and this may benefit Veterans for whom remote treatment options are indicated or preferred. There are no significant risks associated with the proposed telehealth-based protocol - rather, it is expected that this CM option may be lower risk for some Veterans. This substudy will combine the use of an approved "standard of care" treatment option with approved VA telehealth technology (e.g., VVC) and so does not significantly deviate from standard clinical practice. However, due to the use of Veteran-administered oral fluid testing, this treatment protocol would currently only be permissible in the context of research. Participants will be informed of confidentiality and privacy considerations that are unique to telehealth at the start of each session (for example, ensuring that the Veteran has sufficient privacy in their current environment), as is typical of all such clinical interactions.

SUB-STUDY 2: REMOTE PHYSIOLOGICAL MONITORING FOR STATE-DEPENDENT PREDICTORS OF CRAVING AND USE

SUB-STUDY 2 Specific Aim: Establish feasibility of data collection using wearable sensors and identify promising physiological markers of stimulant craving and/or use between treatment encounters.

In this sub-study, I will leverage the existing infrastructure of my CDA research to collect supplemental physiological and activity data via wearable sensors to identify potential real time markers of craving and use. Participants will be recruited through our established recruitment pipeline. Following enrollment in the parent protocol, up to 45 participants will be invited to participate in additional physiological and activity monitoring during the first two weeks of the 12-week treatment interval. Individuals who decline to participate will be asked to share specific concerns contributing to this decision. Those who choose to enroll will be outfitted with a wrist-worn ActiGraph wGT3X-BT wearable activity monitor and Bluetooth-enabled Polar H7 Heart Rate monitor. Together, these medical-grade wearable devices enable high resolution monitoring of heart rate (including R-R intervals), physical activity (including sleep/wake time and related metrics), and compliance without conveying feedback to the wearer. Participants will receive training on routine maintenance of wearable devices, including requirements for recharging/changing batteries. Feedback regarding acceptability of wearable monitoring, as well as problems encountered, will be recorded at the beginning and end of sub-study participation. Devices will be returned at the conclusion of the 2-week recording period, whereupon data will be downloaded and the participant will be compensated \$40. Participants may additionally receive daily reminder calls during the 2-week recording interval to ensure that they are wearing the devices properly and to troubleshoot any problems that may arise. Upon request, participants may receive a copy of a clinical report, generated by ActiLife software, summarizing activity and sleep data from the recording interval.

Data Analytic Plan. The number of participants declining to participate in the sub-study, as well as feedback regarding acceptability of wearable device monitoring will be quantitatively and qualitatively summarized. Data collected through ActiGraph/Polar wearable devices will be reviewed, preprocessed, and analyzed using ActiLife software. The proportion of data rejected due to noncompliance (detected using ActiLife's Wear Time Validation Tool) or poor electrocardiography (ECG) signal quality (determined through visual inspection) will subsequently be computed. Valid data segments will be subject to additional analyses investigating potential markers of high-risk states in wearable data streams. Based on previous work and known cardiovascular effects of stimulants, periods of elevated resting heart rate

are expected to predict self-reported stimulant use and subsequent stimulant-positive urinalysis. For example, periods of elevated heart rate associated with cocaine craving can be distinguished from use events based on duration (30-40 minutes for craving versus 2 hours for use). The number and duration of elevated resting heart rate intervals will be investigated as potential predictors of self-reported and objectively verified stimulant use using a mixed effects logistic regression approach. Additional exploratory features extracted from ECG and activity data (e.g., heart rate variability (linked to craving in alcohol users), sleep efficiency (known to be impaired during early cocaine abstinence), and number/duration of physical activity bouts) may also be considered. These preliminary analyses will serve to identify promising state-dependent markers from wearable data streams for future investigation. Importantly, a mobile interface to be developed under a separate protocol (Pro3566) will support ecological momentary assessment of craving, stress, and substance use and these data will critically inform future efforts to distinguish physiological markers associated with high-risk for use – of relevance to delivery of in the moment interventions – from actual use events.

View: 6 Study Population Summary

Study Population Summary

1.0 * What is the maximum number of subjects you plan to enroll at VAPHS?

215 (Target Sample Size Primary Study = 140; an additional 1-5 Veterans may be invited to participate in Sub-Study 1)

Participants in Sub-Study 2 (n = 45) will already be enrolled in the primary protocol and so are already included in the projected target sample.

2.0

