previously indicated, both VoucherPBCM and TangiblePBCM are already utilized in VA substance use clinics but selection of one variant over the other is currently driven by practical considerations alone. The proposed work will determine if a measurement-based approach to implementation of VoucherPBCM versus TangiblePBCM is indicated and will specifically evaluate the potential of FMDM-aligned neural and cognitive markers to guide clinical decision-making. Actionable consequences of the proposed work are summarized in Table 1; additional alternative outcomes (e.g., evidence of differential treatment response in VoucherPBCM versus TangiblePBCM by CUD severity) are not detailed but may also inform delivery of CM within the VA.

Table 1. Relevance of potential empirical observations to PBCM implementation within VA.

	Finding from the Proposed Research	Recommendation
Hypothesis	Patients with greater FMDM impairment (as indexed by neurocognitive markers) will demonstrate improved treatment outcomes in TangiblePBCM relative to VoucherPBCM.	TangiblePBCM is recommended for patients with greater FMDM impairment.
	Patients with less FMDM impairment (as indexed by neurocognitive markers) will demonstrate improved treatment outcomes in VoucherPBCM relative to TangiblePBCM.	VoucherPBCM is recommended for patients with less FMDM impairment.
Alternative Outcomes	Treatment outcomes are comparable in TangiblePBCM and VoucherPBCM, regardless of level of FMDM impairment.	TangiblePBCM and VoucherPBCM are equally appropriate for all patients.
	Treatment outcomes are improved in TangiblePBCM relative to VoucherPBCM, regardless of level of FMDM impairment.	TangiblePBCM is recommended for all patients.
	Treatment outcomes are improved in VoucherPBCM relative to TangiblePBCM, regardless of level of FMDM impairment.	VoucherPBCM is recommended for all patients.

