In sum, the FMDM model of CM has important implications for personalized treatment delivery and may also reveal novel opportunities to enhance the short- and long-term effectiveness of the intervention. However, key predictions of the model remain to be tested. The current CDA aims to address this knowledge gap by (1) evaluating individual differences in FMDM function as predictors of treatment response in CM variants utilizing concrete (TangiblePBCM) versus abstract (VoucherPBCM) future rewards and (2) examining longitudinal change in neural and cognitive processes underlying putative FMDM-based mechanisms of CM. Ultimately, this line of research aims to improve VA CM programming by clarifying both how and for whom existing versions of PBCM are effective. In particular, understanding the role of FMDM in patient-level outcomes could immediately inform treatment recommendations within VA clinics (wherein both VoucherPBCM and TangiblePBCM are already used). The proposed research may additionally highlight new opportunities to improve CM and aftercare programming through enhanced emphasis on FMDM skill development, maintenance, and generalization. Furthermore, by elucidating neural adaptation within FMDM-related brain networks during CM such mechanisms may be more directly targeted through cognitive training, neurofeedback, or noninvasive brain stimulation in subsequent research.

6.0

Please upload any additional documents:

Name Version

There are no items to display

[View: 2.1 Required Reviews](#)

Required Reviews

1.0

Type of Submission:

New study

If this is a 'New Paper Conversion' please include the MIRB Number:

Please upload a letter certifying that you have made no modifications or amendments in converting this research study from paper to electronic:

2.0 * Requested Review Type:

Name

Exempt

Expedited X

Full IRB Review

Not Human Subject Research

3.0

Please check which of the following Service Lines/Departments/Entities will be impacted or used in the conduct of this study

Upload Letter of Support

Clinical Support

Medical Specialty: Medical Service Line LOS (0.01)

Investigational Drug Service

Imaging

Community Based Care

Patient Care Services

Behavioral Health: BH Service Line LOS (0.01)

Primary Care

Surgical Specialty

Critical Care

Clinical Trials Center

Regulatory Coordinator Support Core

Clinical Coordinator

Support Core

Ancillary Support Core

Data Support Core

Research Registry

Registry Number:

Other

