holds on research activities therefore effectively suspended enrollment for approximately one year. After research activities could be safely resumed, the COVID-19 pandemic also continued to negatively impact recruitment as the majority of outpatient substance use treatment services continued to be offered remotely throughout the remainder of our active enrollment period. This resulted in reduced foot traffic through clinic areas, making it more difficult to connect with potentially eligible participants. While a variety of new recruitment methods were introduced, our final sample size was much smaller than originally projected.

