To address limitations related to the ratio of observations to predictors in the context of our reduced sample size, we revised our predictive analytic approach (Specific Aim 1) to prioritize model stability and interpretability, while framing results as more preliminary in nature. With respect to Aim 1, a revised sample size of ~50 participants was identified as sufficient to support investigation of up to five candidate predictors: e.g., two EEG-derived metrics, one clinical measure, one neurocognitive measure, and treatment condition. Recent simulation-based work (Austin & Steyerberg, 2015) further suggests that as few as two participants per predictor may be adequate, supporting investigation of the original candidate set even within the reduced sample. Two consulting biostatisticians endorsed this revised approach and further recommended modeling repeated binary outcomes over the course of CM treatment to improve power. In line with this recommendation, we modeled 24 repeated binary outcomes per participant, yielding up to $24 \times n$ observations across n participants. However, recognizing that the effective number of independent events remains tied to the number of participants rather than the number of observations, we adopted a two-stage variable selection process to reduce the risk of overfitting. In the first stage, we screened predictors using single-predictor longitudinal logistic regression models, identifying those with theoretically plausible associations with the outcome. This process narrowed our total number of candidate predictors. In the second stage, we applied stepwise forward selection guided by the Akaike Information Criterion (AIC) to construct a parsimonious, interpretable multivariate model. To further assess model robustness and generalizability, we evaluated predictive performance using leave-one-out cross-validation (LOOCV).

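### Table 1 turns comparable outcomes into a recommendation of equal appropriateness, but nothing in the Aim 1 plan can show comparability and no row covers an inconclusive result

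*Combined protocol and SAP*

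**What the plan says.** Section 2, item 5.0 introduces the table with "Actionable consequences of the proposed work are summarized in Table 1". One of its alternative outcomes reads "Treatment outcomes are comparable in TangiblePBCM and VoucherPBCM, regardless of level of FMDM impairment", and the recommendation beside it is "TangiblePBCM and VoucherPBCM are equally appropriate for all patients". Each of the other four rows requires a difference, either at a given level of FMDM impairment or for all patients. The text before the table adds that "additional alternative outcomes (e.g., evidence of differential treatment response in VoucherPBCM versus TangiblePBCM by CUD severity) are not detailed". Later in the same item, the stated use of the work is that "understanding the role of FMDM in patient-level outcomes could immediately inform treatment recommendations within VA clinics".

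The Aim 1 analysis is in section 4.1. It hypothesises a significant interaction between condition and the FMDM measures. The revised method is single-predictor screening, forward selection by AIC and leave-one-out cross-validation, within a per-session longitudinal logistic regression. On size, section 4.1 reports that "our final sample size was much smaller than originally projected" and that "a revised sample size of ~50 participants was identified as sufficient to support investigation of up to five candidate predictors". It describes the revised approach as favouring stability and interpretability "while framing results as more preliminary in nature".

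The text on treatment condition is mixed. The study design description and part of the Aim 1 text speak of including it. The revised plan lists it as one of the example candidate predictors, and those are subject to selection.

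**The concern.** A conclusion that two variants suit all patients equally is an equivalence claim. Here it is made at every level of FMDM impairment. Such a claim needs a statement of how small a difference must be to count as comparable, and an interval narrow enough to exclude anything larger. The plan has neither. Failing to find a difference, or failing to select a term, is a different result and may only reflect a small sample.

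A trial that finds nothing has only one listed row to fall into. If the hypothesised crossover is real but missed, that row would say that matching patients to a variant is unnecessary, which is the question the study was set up to answer. The arm difference is also least precisely estimated among patients with low or high FMDM scores, for whom matching would matter most.

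**Working it through.** **The plan's own power figure.** The documents give no power, margin or precision for Tangible versus Voucher, or for condition by FMDM. The nearest stated figure is for Aim 2, adherence by time: f = 0.12 at N = 140 and f = 0.13 at N = 119, with alpha 0.05 and power 0.80. Assuming a within-person correlation of 0.5 (not stated), the noncentrality is f² × N × 2 / (1 − 0.5).
- N = 140: 0.12² × 140 × 4 = 8.06, with 1 and 138 df, gives power 80.5%.
- N = 119: 0.13² × 119 × 4 = 8.04, with 1 and 117 df, gives power 80.3%.

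These figures reproduce, but they do not bear on the arm comparison.

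**Inputs for the arm comparison.**
- Total of about 50: section 4.1, the size called sufficient for Aim 1. The final number and the split between arms are not given.
- 25 per arm: assumed.
- SD of the percentage of cocaine-negative sessions, 30 to 45 points: assumed.
- True difference of 20 points: illustrative, not a proposed margin.

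**Formulas**, treating each participant's percentage as one observation:
- Standard error of the arm difference: SE = SD × √(2/25).
- Overall 95% half-width: t(0.975, 48 df) × SE, with t = 2.011.
- At ±1 SD of one FMDM measure, in a model with the interaction: the variance doubles, so the half-width is t(0.975, 46 df) × SE × √2, with t = 2.013.
- Miss with a 5% test: the probability that a noncentral t (48 df, noncentrality 20/SE) lies within ±2.011.
- Miss under AIC: condition is kept if 50 × ln(RSS0/RSS1) > 2, which means |t| > √(48 × (e^0.04 − 1)) = 1.40. The miss is the probability of lying within ±1.40.

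| SD (points) | SE | Half-width overall | Half-width at ±1 SD FMDM | Miss, 5% test | Miss, AIC |
|---|---|---|---|---|---|
| 30 | 8.49 | 17.1 | 24.2 | 36.3% | 17.0% |
| 35 | 9.90 | 19.9 | 28.2 | 49.2% | 26.7% |
| 40 | 11.31 | 22.7 | 32.2 | 59.0% | 35.4% |
| 45 | 12.73 | 25.6 | 36.2 | 66.3% | 42.8% |

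At the original 70 per arm, the same formulas give half-widths of 10.0 to 15.0 points overall and 14.2 to 21.3 at ±1 SD. The misses are 2.5 to 25.7% (5% test) and 0.6 to 11.1% (AIC). The row became harder to support when the sample shrank.

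**Whether 24 sessions per person rescue precision.** A per-session simulation compared 40% with 60% success, with within-person correlation set to match the SDs above, so it does not test those SDs independently. Allowing for clustering, the miss was 39 to 69% with a 5% test and 19 to 46% at the participant-level AIC threshold. These are close to the table.

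**The case against.** The strongest reply is that the table is conditional. It says what follows if outcomes are comparable. It never says that a non-significant or unselected term shows they are. That is correct. A reader might infer that the plan itself declares a null to be proof of equivalence, and the documents do not support that reading. Table 1 is significance-section text that section 4.1 never uses, the document says that other outcomes are left out, and the revised Aim 1 results are framed as preliminary. These points limit the weight of the concern but do not remove it. None of them defines comparable, the one example of an omitted outcome is another moderator rather than an imprecise result, and the table was not revised to match the preliminary framing.

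A reader might also infer that condition will be dropped from the model. The documents do not settle this, because some passages speak of including it and the revised plan lists it as a candidate. Selection may omit it, and no more than that can be said.

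The figures do not model the planned procedure. They use a participant-level percentage and assumed inputs, without the screening stage. The risk also depends on the rule. In least-squares simulations with five FMDM measures under AIC, a true crossover of 20 points per SD was missed in only 7 to 18% of trials, and a true null left nothing flagged in only about 34%. In that setting, false selection is the larger risk. An AIC that ignored within-person correlation would drop a true 20-point difference in only about 3 to 7%, although section 4.1 itself accepts that information is limited by the number of people. So the chance of a null is uncertain. How to read one if it occurs is still undefined.

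Finally, both variants are already in VA use, so the immediate practical harm of the wording is modest.

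**Conclusion.** The point holds as a gap between a listed recommendation and what the planned analyses can show. Comparable is undefined, the Aim 1 methods look only for differences, and an inconclusive result has no listed row, so a null could be taken as equivalence. With an assumed 25 per arm and SD of 30 to 45 points, the 95% interval would extend about 17 to 26 points either side of the estimate overall, and 24 to 36 points at ±1 SD of an FMDM measure. A true 20-point difference would be missed in 36 to 66% of trials with a 5% test, or 17 to 43% under participant-level AIC. These sizes rest on the assumed arm split and SDs. The absence of a margin, an interval rule and an inconclusive row rests on the text alone. The change should be made, but this is a matter of interpretation and reporting, not a fault that invalidates the Aim 1 analysis.

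**What to change.** 1. Add a row to Table 1: neither comparability nor a difference shown; inconclusive; no recommendation.
2. State that a non-significant or unselected condition term, or condition by FMDM term, does not establish comparability.
3. Report the Tangible minus Voucher difference in the probability of a cocaine-negative session with its 95% confidence interval. Take it from a per-session logistic model that keeps condition whether or not AIC selects it and that allows for within-person correlation. Give it overall, and at low and high values of the FMDM measures carried into the reported models.
4. Keep the equal-appropriateness recommendation only if a margin was set before results were seen and the intervals lie within it. Otherwise drop it. Section 4.1 describes the revised modelling in the past tense, so a margin chosen now may come too late.

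The cost is one table row, one sentence and a few more intervals from a model of the kind already fitted. No new data are needed. The downside is that an equivalence statement is probably unavailable at this size.
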